1.1 General Introduction

The Mollii suit is a new technology of electrical stimulation in the form of whole-body garment with multiple electrodes individually programmed to stimulate the selected muscles. Based on preliminary studies, it is suggested that the Mollii suit improves spasticity. Recent studies also proposed that it improves mobility, gait, function and quality of life. However, these studies are based on qualitative and subjective measures.

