1.2.4 Rationale for Study Design

This is a single-centre study that compares subjects before and after the intervention. As a wide range of age group is used in the study population, comparison is made in gait in the same individual.

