2.2 Primary Objectives

The primary objective is to assess the effectiveness of the Molli suit in improving gait in children with cerebral palsy, GMFCS I-III.

Change in Gait Profile Score will be computed as primary outcome measure. Other measurements obtained in the gait analysis include Gait deviation index, gait speed and cadence etc.

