4.1 Randomisation and Blinding

Randomisation and blinding will not be performed.

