4.3.2 Study Visits and Procedures

Baseline

Prior to commencement of intervention (within 2 weeks prior to fitting of Mollii suit), the child will undergo:

I. An instrumented 3-dimensional gait analysis

For the 3-dimensional gait analysis, patient is required to walk on a walkway of approximately 8 to10 metres long with 2 force-plates along the walkway. The patient will have skin markers placed on their body, majority on the lower extremities following the Plug-in Model marker placement model by physiotherapist. The patient will be required to walk barefoot with and/or without walking aid repeatedly along the walk-way until 6 to 8 successfully clean strike on the force plate. The VICON infra-red camera system will capture the trial and after which, the data will be analysed by the study team member.

II. Questionnaire (Annex I and II)

This consists of 2 sets of self-administer questionnaire for parent and child respectively. The child's questionnaire on demographics, patient's perception on own health, mobility, emotions, activity (EQ-5D, ICF see below) and pain. The parent's questionnaire consist items on demographics, parent's perception on child's health, mobility, emotions, activity and resource use.

III. EuroQoL (EQ-5D)

EQ-5D is a standardised measure of health status in order to provide a simple, generic measure of health for clinical and economic appraisal.^{xiv} The EQ-5D-Y is the child-friendly

version. EQ-5D consists of the descriptive system and the EQ visual analogue scale (EQ VAS). The descriptive system comprises 5 dimensions. The EQ VAS records the respondent's self-rated health on a vertical, visual analogue scale where the endpoints are labelled 'The best health you can imagine' and 'The worst health you can imagine'. Parent or caregiver will be answering EQ-5D based on what they think the child feels. Whenever possible, for a child who can communicate and self-report assessment, EQ5D-Y will be used.

IV. ICF-CY

The WHO International Classification of Functioning, Disability and Health, Children & Youth version (ICF-CY) is a measure to grade function of activities of daily living (ADLs).^{xv} Few ICF-CY categories have been selected and graded based on the frequency, intrusiveness or severity of the specific impairment. (refer Table below).^{xvi}

The ICF-CY categories assessed and grading for each patient before and after intervention

ICF-CY categories	Illustration of grading

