6.5 Blinding

Blinding is not done.

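### Nothing keeps the person who processes the gait recordings from knowing which is pre and which is post, so a processing lean can enter the uncontrolled primary change

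*Protocol*

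**What the plan says.** The primary outcome is set in Protocol 2.2: "Change in Gait Profile Score will be computed as primary outcome measure". Section 1.2.4 describes the design: "This is a single-centre study that compares subjects before and after the intervention". There is no comparison group.

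On masking, section 4.1 states "Randomisation and blinding will not be performed" and section 6.5 states "Blinding is not done". Neither makes an exception for outcome assessment or for work on stored data.

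On how the score is produced, section 4.3.2 has skin markers placed "following the Plug-in Model marker placement model by physiotherapist". The child walks, with and/or without an aid, until 6 to 8 clean force-plate strikes are obtained. The section continues: "The VICON infra-red camera system will capture the trial and after which, the data will be analysed by the study team member". It does not mention coded files, processing order, or whether the analyst may also have run the session. The second gait analysis is at Visit 3, when the suit is handed back (Table 2).

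The general safeguards are anonymisation of identifiable data (8.1, 12.2) and monthly data-quality checks (11). Neither hides visit order.

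**The concern.** Section 1.1 notes a limit of the earlier suit studies: "However, these studies are based on qualitative and subjective measures". Instrumented gait analysis answers that limit only as far as human judgement is kept out of the steps between recording and score. The cameras are objective. Deciding which walks and cycles are used, and how they are processed, is at least partly a matter of judgement. Section 4.3.2 gives no rule for that choice beyond the number of clean strikes.

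In a controlled trial, a lean that affects both arms alike largely cancels. Here nothing cancels it: a systematic tendency to favour better-looking cycles at the second session adds directly to the mean change and looks the same as benefit. An analysis plan applied to finished scores cannot undo this, so masking has to be fixed before processing begins.

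**Working it through.** **Inputs.** Number of children: up to 20 (Protocol 3.1). Target difference 1.6, SD 2.4 between pre and post (read as the SD of the change), two-sided paired t-test, significance level 0.05, power 80% (9.1).

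**1. Reproduce the plan's own size.** Section 9.1 prints no number of children, so the check is against the 20 in 3.1. For a paired t-test, df = n − 1 and the non-centrality is (1.6/2.4)·√n.
- n = 19: non-centrality 2.906, power 0.785.
- n = 20: non-centrality 2.981, power 0.807.

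The smallest n reaching 80% is 20. The sample size reproduces and is not in question.

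**2. Effect of a lean when there is no true change.** Let b be a systematic shift in the change caused by processing.
- Standard error = 2.4/√20 = 0.537.
- Critical value t(0.975; 19) = 2.093, so an observed mean change of 2.093 × 0.537 = 1.12 units is significant.
- Non-centrality = b/0.537. The rejection probability is the non-central t probability beyond ±2.093.

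| Assumed lean b | Share of 1.6 | Non-centrality | P(p < 0.05) |
|---|---|---|---|
| 0 | 0% | 0 | 5.0% |
| 0.3 | 19% | 0.559 | 8.3% |
| 0.5 | 31% | 0.932 | 14.3% |
| 0.8 | 50% | 1.491 | 29.4% |

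The values of b are assumptions; the protocol supplies none. The estimate itself is shifted by b whatever the true effect is.

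**3. Marker placement, kept separate.** Random marker error with an assumed SD s per session, if not already in the 2.4, gives an SD of change of √(2.4² + 2s²).
- s = 0.5: SD 2.50, power 77.4% with 20 children.
- s = 1.0: SD 2.79, power 68.3%.
- If the 2.4 already contains this error, power stays at 80.7%.

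This is loss of precision. It becomes bias only if the error differs systematically between the two sessions.

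**The case against.** Four objections deserve weight.

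*The protocol does not say that the analyst knows the visit.* Correct. One of the two no-blinding statements stands under treatment, the other is a single general line, and neither mentions data processing. A reader might infer that staff do know the order and that bias does enter. The text supports only that nothing prevents the first and that the second can happen. The anonymisation in 8.1 and 12.2 does not change this, because removing identifiers leaves visit order visible.

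*The score comes from camera-captured kinematics with an acceptance rule of 6 to 8 clean strikes.* This limits the room for judgement and is a reason to expect a small lean. It does not remove the room: the protocol does not say which cycles are used, or how walks with and without an aid are handled. That cycle selection is discretionary is my reading of an unspecified step, not a statement in the protocol.

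*The physiotherapist is not tied to the child.* A reader might infer that different people will place the markers at the two visits and so bias the result. The protocol is silent on this; it neither plans nor excludes it. The expected effect is noise, which the SD of 2.4 may already include. It does not support a claim of bias.

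*Masked processing achieves little in an open single-arm study.* It leaves regression to the mean, practice, time effects and the child's expectations untouched. It also cannot mask marker placement or the clean-strike decision, which is made live while the child walks. All of that stands. It bounds the benefit, but it is no reason to leave an avoidable source of error in place.

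**Conclusion.** The point holds as a conduct weakness worth correcting. Blinding is ruled out without exception, a study team member analyses the recordings, and the design has no control arm, so a processing lean can pass undiluted into the primary result. Its size cannot be derived from the documents. On the protocol's own SD and number of children, assumed leans of one fifth to one half of the target difference would raise the false-positive rate from 5% to between about 8% and 29%. These figures rest on reading 2.4 as the SD of the change, on all 20 children being analysed, and on the assumed leans. They show sensitivity and do not estimate bias that has occurred.

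The documents do not support saying that staff know the visit, that bias is present, or that marker placement biases the change.

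**What to change.** Keep the open-label design and state in 4.1, 4.3.2 and 6.5 that:

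1. Each recording has a technical usability check at capture, without scoring, so that an unusable baseline is found before treatment starts.
2. Recordings are then coded to hide child and visit. An existing team member who did not run that child's gait sessions selects cycles and computes the Gait Profile Score, in mixed order and under a written cycle-selection rule. Codes are broken only after scores are locked.
3. The baseline of a child who withdraws is coded and processed in the same pool. Section 4.4.2 provides no further gait analysis for such children, so a rule that waits for both recordings would leave their baselines unscored.

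Optionally, the same physiotherapist places a child's markers at both sessions where possible. This is a precision measure, not a correction of bias.

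The cost is protocol wording, a little file handling and a delay of some weeks in scoring baselines. No new assessor, visit or equipment is needed. Nothing in the protocol depends on early baseline scores: eligibility (3.3, 3.4) does not use the Gait Profile Score, and no interim analysis is described.

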4.3.4 Post Study Follow up and Procedures

Immediately after intervention, child will undergo instrumented 3- dimensional gait analysis and objective assessments, and complete a questionnaire on health outcome measures and feasibility/ acceptability outcomes.

1 months after intervention period, child will undergo objective assessments, and complete a questionnaire on health outcome measures and feasibility/ acceptability outcomes.

4.4 Discontinuation/Withdrawal

4.4.1 Discontinuation Criteria

Study intervention will be discontinued if subject is unable to tolerate the Mollie suit.

4.4.2 Discontinuation Visit and Procedures

Subjects may withdraw voluntarily from participation in the study at any time. If withdrawal occurs, subjects will still be asked to complete a questionnaire to study the reason for withdrawal. No gait analysis and other objective assessments will be done.

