2.3 Secondary Objectives

The secondary objective is to evaluate the acceptability, tolerance and compliance of the Molli suit in children with cerebral palsy.

2.4 Potential Risks and Benefits:

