3.5 Subject Replacement

Subjects who drop out will not be replaced.

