4 STUDY DESIGN

This study will evaluate the effectiveness of improving gait with the use of the Mollii suit in children

with cerebral palsy with instrumented 3-dimensional gait analysis and objective standardised assessment tool at pre-intervention and at 1 month post intervention.

This study will evaluate change in gait and function following a four week intervention period using a protocol of wearing the Mollii suit for one hour every day for four weeks.

This study also evaluates the feasibility of the use of the Mollii suit intervention protocol by conducting qualitative interviews with parents immediately and 1 month after the intervention. Information on compliance, perception of acceptability, benefits or concerns, practicalities, cost and likelihood of using the intervention in the future will be collected.

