7.5 Complaint Handling

If there is any complaint of the Mollii suit, the Principal Investigator will be informed immediately to rectify the issue. If the subject is unable to tolerate the Mollii suit, the study will be discontinued.

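### No acceptability questionnaire or interview is scheduled for families who stop early, so a summary of the acceptability ratings could be biased upwards

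*Protocol*

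**What the plan says.** Protocol section 2.3 states: "The secondary objective is to evaluate the acceptability, tolerance and compliance of the Molli suit in children with cerebral palsy".

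The acceptability data have two sources, both tied to the end of the intervention. Section 4 plans "conducting qualitative interviews with parents immediately and 1 month after the intervention". Section 4.3.4 has the child "complete a questionnaire on health outcome measures and feasibility/ acceptability outcomes", again immediately and 1 month after the intervention. Table 1 and section 4.3.2 show the same two time points and no others.

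For withdrawal, section 4.4.2 names one instrument: "subjects will still be asked to complete a questionnaire to study the reason for withdrawal". It then adds: "No gait analysis and other objective assessments will be done".

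On intolerance, section 4.4.1 reads: "Study intervention will be discontinued if subject is unable to tolerate the Mollie suit". Section 7.5 reads: "If the subject is unable to tolerate the Mollii suit, the study will be discontinued". Section 3.5 adds: "Subjects who drop out will not be replaced".

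During the 4 weeks, parents keep a daily log of compliance, activity and adverse effects, and the child records pain (Table 1, section 4.3.2).

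**The concern.** Whether an acceptability rating is collected depends on something close to acceptability itself. A family that finds the suit hard to live with is more likely to stop. Once it has withdrawn, no scheduled step asks it the questions put to the families who carried on. Section 4 lists what the feasibility data should cover, including practicalities, cost and the likelihood of future use. Nothing says that a form on the reason for withdrawal covers these.

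At stake is the feasibility conclusion, one of the two aims in section 1.2.1. This is a matter of data collection: an analysis plan can set a denominator later, but it cannot supply ratings that nobody asked for. The point does not concern the gait analysis.

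**Working it through.** **Step 1. What is scheduled for whom.**

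| Source | Child who completes 4 weeks | Child who withdraws early |
|---|---|---|
| Daily log: compliance, activity, adverse effects, pain | Yes | Up to the day of stopping |
| Feasibility/acceptability questionnaire | Immediately and at 1 month | Not scheduled, not excluded |
| Parent interview | Immediately and at 1 month | Not scheduled, not excluded |
| Reason-for-withdrawal questionnaire | Not applicable | Yes (4.4.2) |
| Gait analysis and other objective assessments | Yes, per Table 1 | Excluded (4.4.2) |

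The gap is in the second and third rows. The first and fourth rows show that early stoppers still contribute some information on tolerance and compliance.

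**Step 2. Is the withdrawal form the same instrument?** Section 4.3.2 gives annex numbers to its questionnaires: I and II at baseline, IV and VI immediately after the intervention, V and VII at 1 month. Section 4.4.2 cites no annex. That suggests a different form but does not prove it, because the items of neither form are shown.

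**Step 3. Inputs for size.** The Protocol gives the enrolment (up to 20, section 3.1). That number agrees with the inputs in section 9.1: a two-sided paired t-test at 0.05, difference 1.6 and standard deviation of the change 2.4, gives 80.7% power with 20 children and 78.5% with 19. It is not in dispute and serves here only as the denominator. The Protocol gives no withdrawal rate, no acceptability rate and no binary definition of acceptability. These are my assumptions:

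- w, early stops: 0, 2, 4 or 6 of 20.
- a, share of those who stay who find the suit acceptable: 90%.
- b, share of early stoppers who find it acceptable: 0% or 50%.

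**Step 4. Formula.** Share among all 20 = (a × (20 − w) + b × w) / 20. A summary of those who stayed gives a, so the overstatement is (w / 20) × (a − b).

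| Early stops | All 20, b = 0% | Overstatement | All 20, b = 50% | Overstatement |
|---|---|---|---|---|
| 0 | 90% | 0 points | 90% | 0 points |
| 2 | 0.9 × 18 / 20 = 81% | 9 | (16.2 + 1) / 20 = 86% | 4 |
| 4 | 0.9 × 16 / 20 = 72% | 18 | (14.4 + 2) / 20 = 82% | 8 |
| 6 | 0.9 × 14 / 20 = 63% | 27 | (12.6 + 3) / 20 = 78% | 12 |

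If early stoppers would answer like the others (b = a), the overstatement is zero for any w. Each child is 1/20 = 5 percentage points, so a few stops are enough to move the result.

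**Step 5. Which procedures apply after intolerance?** Section 4.4.1 stops the intervention. Section 7.5 says that the study is discontinued. Section 4.4.2 speaks of voluntary withdrawal from the study. Its place directly after 4.4.1, together with 7.5, makes it plausible that an intolerant child follows 4.4.2. Read alone, 4.4.1 would let that child stay in the study and attend the post-intervention visit. The three sections do not settle it.

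**The case against.** The strongest reply is that early stoppers are not lost. The withdrawal questionnaire asks why they stopped, and for a child who could not bear the suit that answer is itself information on tolerance and acceptability. The daily logs cover compliance, adverse effects and pain up to stopping. Section 4.4.2 excludes only gait analysis and other objective assessments, so a coordinator could still give the acceptability questionnaire. All of this stands, and it narrows the point to acceptability ratings and interviews. It does not close the gap: what is merely permitted may not be done, and reasons for stopping cannot be set beside the other families' ratings unless the items match.

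Three stronger readings are tempting but unsupported:

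- *Acceptability is defined on completers and will look too favourable.* No section sets an analysis population for the secondary objective. An analysis plan that is not shown may do so, and may count the withdrawal reasons. With few stops, or similar views among stoppers, there is little or no bias.
- *Compliance is overstated in the same way.* That would need the stoppers' logs to be discarded, which no section says.
- *Every intolerant child is sent down the withdrawal route.* This is an inference from three sections that do not agree.

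Nor does the rule against replacing dropouts add to the concern. If anything, it keeps them visible against the number enrolled.

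**Conclusion.** The point holds in a limited form. As scheduled, the acceptability questionnaire and interview are not collected from families who withdraw, so a summary of those data would rest mainly on children who stayed in and could be biased upwards. The illustrated range is 0 to 27 percentage points. It rests entirely on assumed counts and an assumed yes/no rating, and the upper end needs 6 of 20 children to stop with none of them finding the suit acceptable. Tolerance and compliance are less exposed. This is a cheap improvement to data collection for a secondary objective, not a fault that undermines the trial.

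**What to change.** 1. In section 4.4.2, offer every family that stops early the existing Visit 3 feasibility/acceptability questionnaire together with the reason-for-withdrawal questions. This fits the present text, since it adds no objective assessment.
2. In the same place, state that the study diary is collected when the suit is returned.
3. In section 9.2 or the analysis plan, report acceptability and tolerance for all children fitted with the suit, and show the number of early stops and their reasons alongside the ratings. Detailed counting rules can be left to the analysis plan.
4. Reconcile sections 4.4.1, 4.4.2 and 7.5, so that it is clear which study procedures apply to a child who stops for intolerance.

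The cost is a few sentences. The questionnaire already exists, and no visit is needed beyond returning the suit. Reported acceptability may be lower, and some withdrawing families may decline, as they are free to do. The number who decline should be reported, because the gap will be reduced rather than removed.

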Immediately after intervention, child will undergo instrumented 3- dimensional gait analysis and objective assessments. Child and parent complete a questionnaire (Annex IV and VI) on health outcome measures and feasibility/ acceptability outcomes (refer Table 1).

1 months after intervention period, child will undergo objective assessments. Child and parent complete a questionnaire (Annex V and VII) on health outcome measures and feasibility/ acceptability outcomes (refer Table 1).

Table 2: SUMMARY OF STUDY VISITS

VIST 1:	Pre-intervention assessments: 
- Instrumented 3-dimensional gait study- Questionnaires (include EQ-5D, ICF)- GMFM- FAQ- 10m walk test- GAS	Patient will be charged for one PT session per standard care. Gait study is FOC
VISIT 2:	Collection of Mollii suit, settings for Mollii suit Signing of loan agreement	
@HOME 4WEEKS	Patient will wear Molli suit at home daily 1 hour for 4 weeks. Patient/ parent keep log logs of compliance use, pain and adverse effects.	
VISIT 3	Return Mollii Suit Post-intervention assessments: 
- Instrumented 3-dimensional gait study- Questionnaires (include EQ-5D, ICF)- GMFM	Patient will be charged for one PT session per standard care. Gait study is FOC

	
 - FAQ - 10m walk test - GAS 	
VISIT 4 (1 MTH LATER)	1month post-intervention assessments: 
 - Questionnaires (include EQ-5D, ICF) - GMFM - FAQ - 10m walk test 	Patient will be charged for one PT session per standard care.

4.3.3 Final Study Visit:

As per section 4.3.2

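### The protocol leaves unsettled whether a child who stops the suit for intolerance, but does not withdraw, still has the post-intervention gait analysis

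*Protocol*

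**What the plan says.** Three places in the protocol bear on a child who cannot tolerate the suit.

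- Section 4.4.1: "Study intervention will be discontinued if subject is unable to tolerate the Mollie suit".
- Section 7.5: "If the subject is unable to tolerate the Mollii suit, the study will be discontinued".
- Section 4.4.2, the only text under the heading on discontinuation procedures, opens with "Subjects may withdraw voluntarily from participation in the study at any time". It asks for a questionnaire on the reason for withdrawal and ends with "No gait analysis and other objective assessments will be done".

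The general schedule is in sections 4.3.2 and 4.3.4: "Immediately after intervention, child will undergo instrumented 3- dimensional gait analysis and objective assessments". Tables 1 and 2 list one gait analysis after baseline, at Visit 3, and none at the visit one month later. Table 2 also lists "Return Mollii Suit" at Visit 3, after the four weeks at home. Section 4 states "This study will evaluate change in gait and function following a four week intervention period", but it also places the second gait analysis one month after the intervention, which does not agree with the tables.

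Section 3.5 adds "Subjects who drop out will not be replaced".

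**The concern.** Stopping a treatment and leaving a study are different events, and here the difference decides whether the primary outcome is collected. Section 4.4.1 describes the first and section 7.5 the second, for the same child. Section 4.4.2 does not mention intolerance, so site staff cannot tell whether its exclusion of gait analysis applies.

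If it is applied, the missing gait data are missing because of the suit. Change in Gait Profile Score (section 2.2) would then come only from children who tolerated the device, with no control group (sections 1.2.4 and 4.1). Intolerance is foreseen: section 2.4.1 names discomfort, tingling and allergic reaction, and tolerance is part of the secondary objective in section 2.3. The daily log and the withdrawal questionnaire can show who stopped and why, but not how their gait changed. A statistical analysis plan can choose an analysis set, but it cannot recover a gait analysis that was not done.

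**Working it through.** **Side by side.** Sections 4.4.1 and 7.5 attach different consequences to one event. Taken with 4.4.1, a child who stops the suit remains a study subject, and nothing expressly removes the post-intervention assessments. Taken with 7.5, the child's participation ends, and 4.4.2 is the only procedure on offer, without gait analysis. No section says which applies.

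**The plan's own figure.** Inputs from section 9.1: two-sided paired t-test, alpha 0.05, power 80%, difference 1.6, SD 2.4 (read as the SD of the paired change). Standardised effect = 1.6/2.4 = 0.667. The exact calculation (noncentral t, n − 1 degrees of freedom) gives n = 20 as the smallest size reaching 80%, with power 80.7%. The up-to-20 of section 3.1 is reproduced and holds no reserve: with 19 children measured, power is 78.5%.

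**Assumed range.** The protocol gives no stopping rate and no outcome for stoppers. Assume 20 enrolled, completers changing by 1.6 in the direction of benefit (the protocol's minimal important difference, not a forecast), and k = 2, 4 or 6 stoppers changing by s = 0, 0.8 or 1.6.

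- All-children mean = (1.6 × (20 − k) + s × k)/20
- Excess = 1.6 − all-children mean
- Completer standard error = 2.4/√(20 − k) = 0.566, 0.600, 0.641 for k = 2, 4, 6

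| k | s | All-children mean | Excess | Excess / SE |
|---|---|---|---|---|
| 2 | 0 | 1.44 | 0.16 | 0.28 |
| 4 | 0 | 1.28 | 0.32 | 0.53 |
| 6 | 0 | 1.12 | 0.48 | 0.75 |
| 2 | 0.8 | 1.52 | 0.08 | 0.14 |
| 4 | 0.8 | 1.44 | 0.16 | 0.27 |
| 6 | 0.8 | 1.36 | 0.24 | 0.37 |
| any | 1.6 | 1.60 | 0 | 0 |

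**Power.** Completers only, exact calculation at n = 18, 16, 14: 76.0%, 70.3%, 63.6%. With all 20 measured, the mean is as in the table and the variance is 2.4² + f(1 − f)(1.6 − s)², where f = k/20. For k = 2, s = 0 this is 5.76 + 0.09 × 2.56 = 5.99, so SD 2.45. The resulting power for k = 2, 4, 6 is:

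- s = 0: 70.4%, 59.0%, 47.4% (simulation: 70.5%, 59.1%, 47.0%)
- s = 0.8: 76.2%, 71.4%, 66.2% (simulation: 76.3%, 71.5%, 66.2%)
- s = 1.6: 80.7% throughout

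Measuring everyone therefore lowers power when stoppers do not change, because the mean being tested is smaller. It raises power slightly at s = 0.8, and more at s = 1.6.

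**The case against.** A coherent reading exists. Section 4.4 covers discontinuation and withdrawal together: 4.4.1 gives the criterion, 4.4.2 the procedure, and 7.5 can be taken to say that participation ends. On that reading the three sections agree that a child who stops is not assessed. This is possible, but the text does not establish it, since 4.4.2 names only voluntary withdrawal. Were it the intention, outcome collection would end because of intolerance, which is the selection at issue.

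A reader might go further and infer that the visit schedule in 4.3.2 and 4.3.4 contradicts 4.4.2. It does not. A general schedule and an exception for withdrawal can stand together. Sections 4, 4.3.2 and 6.3 fix a four-week period, so gait analysis straight after the intervention most naturally means after those four weeks. A reader might equally infer that the protocol plainly denies gait analysis to every child who stops, but 4.4.2 does not say that either.

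The size is hypothetical. Section 2.4.1 expects minimal risk, section 3.3 requires the child to agree to wear the suit, and even the largest excess shown is below one standard error. Overstatement also presumes that the target is the effect in all enrolled children. The protocol does not say so expressly, though neither the hypothesis nor the primary objective is confined to children who tolerate the suit. These points limit the weight of the concern but do not settle the text.

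**Conclusion.** The point holds as an unresolved ambiguity. The direct conflict is between sections 4.4.1 and 7.5, and it is compounded by the unclear reach of section 4.4.2. If 7.5 and 4.4.2 are followed, the primary outcome is lost selectively and cannot be repaired in analysis.

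The size cannot be known from the document. Under the assumed 2 to 6 stoppers of 20 with no change, completers alone would overstate the all-children mean by 0.16 to 0.48 points, and by half that if stoppers change by 0.8. There is no bias if nobody stops or if stoppers change as much as completers. The power figures do not argue for or against the current text, because their direction depends on how stoppers fare.

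This is a cheap improvement to outcome collection. It takes no position on when or why the suit is stopped.

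**What to change.** Reconcile sections 4.4.1, 4.4.2 and 7.5 for outcome collection only, leaving the rule for stopping the suit as it is.

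- Limit the sentence excluding gait analysis in 4.4.2 to children who withdraw from the study.
- State that children who stop the suit without withdrawing stay on the scheduled post-intervention assessments, with Visit 3 at the planned end of week 4, so that the interval from baseline matches that of completers.
- Report how many children stopped and how many were not assessed. The choice of analysis set can stay with the statistical analysis plan.
- In the same revision, reconcile section 4, which puts the gait analysis one month after the intervention, with Tables 1 and 2 and sections 4.3.2 and 4.3.4, which put it immediately after.

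The cost is wording in a few sections. Gait analysis is already budgeted for 20 subjects (section 15) and is free to families (Table 2). There are downsides. Families of children who stopped would be asked to attend, and would meet the physiotherapy charge that Table 2 sets for Visits 3 and 4 unless it is covered. Some will decline. The mean change may be smaller and power lower: about 70.5% against 76.0% for completers only, if 2 of 20 stop and do not change.
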